4.4.2.1.2 Maximum Overall Intensity

Maximum overall intensity is derived from the daily intensities as described in Section 4.4.2.1.1 and is calculated as the maximum of the daily intensities over the period considered.

4.4.2.1.3 Presence

Presence is derived from the maximum overall intensity on the period considered:

- None: No presence
- Grade 1, Grade 2, or Grade 3: Presence

- Missing: Missing presence

Subjects with at least 1 non-missing presence (maximum overall intensity ≥ 0) for a specific endpoint will be included in the analysis. Conversely, those without a non-missing presence will not be included in the analysis of the endpoint.

4.4.2.1.4 Time of Onset

Time of onset is derived from the daily intensities as described in Section 4.4.2.1.1. It corresponds to the first day with intensity of Grade 1, Grade 2, or Grade 3 during the solicited period (D0 to D07) after vaccination(s).

Note: If a reaction is not continuous (ie, reaction occurs over 2 separate periods of time intervened by at least 1 daily intensity Missing or None) then the time of onset is the first day of the first occurrence during the solicited period (D0 to D07) after vaccination(s).

4.4.2.1.5 Number of Days of Occurrence

Number of days of occurrence over the solicited period (D0 to D07) considered is derived from the daily intensities as described in Section 4.4.2.1.1. It corresponds to the number of days with 1 of daily intensities of Grade 1, Grade 2, or Grade 3. Number of days of occurrence on the solicited period with a specified intensity (eg, Grade 3) may also be derived.

4.4.2.1.6 Overall Number of Days of Occurrence

If a reaction is ongoing at the end of the solicited period, then the overall number of days of occurrence after vaccination(s) is derived from the daily intensities and the stop date of the reaction after the end of the solicited period. The overall number of days of occurrence is:

$$(\text{The stop date of the solicited event} - \text{last vaccination date}) + (\text{number of days of occurrence within the solicited period}) - \text{length of the solicited period} + 1$$

If stop date of the solicited reaction is missing or incomplete (contains MD), the overall number of days of occurrence will be considered as Missing.

4.4.2.1.7 Ongoing

Ongoing is derived from the last daily intensity of the solicited period as described in Section 4.4.2.1.1 and the maximum intensity on the ongoing period. The Investigator's ongoing flag is not used because the measurement would determine the ongoing status of the reaction.

If the last daily intensity at D07 of the solicited period is at least Grade 1 and maximum intensity on the ongoing period is also at least Grade 1, then the reaction is considered ongoing. In any other cases the reaction will not be considered as ongoing.

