4.3.2.3.3 Unsolicited Adverse Events

In addition to recording solicited reactions, subjects or subjects' parent / guardian will be instructed to record any other medical events that may occur. Space will be provided in the diary card for this purpose.

Information on SAEs will be collected and assessed throughout the study, from the time of vaccination until 6 months after the last vaccination. Any SAE occurring at any time during the study will be reported by the Investigator in the CRB according to the completion instructions provided by the Sponsor; this includes checking the "Serious" box on the AE (electronic) case report form (CRF) and completing the appropriate Safety Complementary Information CRFs. All information concerning the SAE is to be reported either as part of the initial reporting or during follow-up reporting if relevant information became available later (eg, outcome, medical history, results of investigations, copy of hospitalization reports. See protocol for further details on SAE reporting.

For each unsolicited AE (whether serious or non-serious), the following information is to be recorded:

- Start and stop dates^a
- Intensity of the event

For measurable unsolicited AEs that are part of the list of solicited reactions, the size of the AE as well as the temperature for fever will be collected and analyzed based on the corresponding scale used for solicited reactions (see [Table 4.1](#) and [Table 4.2](#)).

All other unsolicited AEs will be classified according to the following intensity scale:

- Grade 1: A type of AE that is usually transient and may require only minimal treatment or therapeutic intervention. The event does not generally interfere with usual activities of daily living

^a The stop date of all related AEs will be actively solicited. For other events, the Investigator will provide the stop date when it becomes available. AEs for which no stop date was obtained during the course of the study will be considered as ongoing at the end of the study.

- Grade 2: A type of AE that is usually alleviated with additional therapeutic intervention. The event interferes with usual activities of daily living, causing discomfort but poses no significant or permanent risk of harm to the research participant
- Grade 3: A type of AE that interrupts usual activities of daily living, or significantly affects clinical status, or may require intensive therapeutic intervention

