4.4.2 Safety

4.4.2.1 Solicited Reactions

4.4.2.1.1 Daily Intensity

All daily records for solicited reactions will be derived into daily intensity according to the following classification: None, Grade 1, Grade 2, Grade 3, or Missing.

For the derivation of daily intensities, the following sequential steps will be applied:

- 1) Solicited reactions (except Fever/Pyrexia) with an Investigator presence recorded as "No" and with all daily records missing, then all daily intensities will be derived as None
- 2) For a temperature partially missing after decimal point, the data will be analyzed replacing "MD" (missing data) by zero. For example, a "39.MD" daily temperature will be considered as "39.0°C" at the time of analysis.
- 3) For non-measurable (NM) solicited reactions, daily intensities will correspond to daily records reported in the clinical database. For measurable solicited reactions the daily measurements reported in the clinical database will be converted based upon the intensity scales defined in the protocol; this assumes a reaction that is too large to measure (NM) is Grade 3.

Note: The maximum intensity on the ongoing period is derived from the record of the maximum intensity / measurement after the end of the solicited period following the rule described above.

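### SAP 4.4.2.1.7 handles a Missing D07 grade or Missing post-D07 maximum as None, so a solicited reaction with a known later stop date keeps at most 7 or 8 days

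*SAP*

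**What the plan says.** SAP 4.4.2.1.7 derives ongoing status from two entries: if the D07 intensity "is at least Grade 1 and maximum intensity on the ongoing period is also at least Grade 1, then the reaction is considered ongoing". Everything else is excluded: "In any other cases the reaction will not be considered as ongoing". The site's own indicator is set aside: "The Investigator's ongoing flag is not used because the measurement would determine the ongoing status of the reaction".

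SAP 4.4.2.1.6 makes the extension beyond D07 depend on that status: "If a reaction is ongoing at the end of the solicited period, then the overall number of days of occurrence" is built from the daily intensities and the stop date. If the stop date is missing or incomplete, "the overall number of days of occurrence will be considered as Missing". The section gives no value for a reaction that is not ongoing. SAP 4.4.2.1.5 counts the days graded 1 to 3 within D0 to D07.

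SAP 4.4.2.1.1 allows a daily intensity to be "None, Grade 1, Grade 2, Grade 3, or Missing". It fills wholly missing daily records only when the Investigator recorded the reaction as absent and every daily record is missing. It also completes a temperature lacking its decimal and sets a reaction too large to measure to Grade 3. SAP 5.3.1 replaces nothing, and 5.3.1.4 refers missing solicited intensities back to 4.4.2.1.1.

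**The concern.** No rule covers a single blank D07 grade or a blank post-D07 maximum. Both fall into the residual clause of 4.4.2.1.7, where Missing and None lead to the same result. A recorded None is evidence that the reaction had ended or fallen below threshold; a blank is not.

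The reason given for not using the Investigator's flag is that the measurement settles the matter, but when the entry is blank there is no measurement. Four of the seven solicited reactions in SAP Tables 4.1 and 4.2 (pain, headache, malaise, myalgia) are graded by the subject and not measured at all.

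At stake is the overall number of days of occurrence, the SAP's derivation for reactions that outlast D07. A shortened value looks like a genuine short duration, so nobody reading the output would know that a later stop date had been ignored.

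**Working it through.** The documents state no figure on this point, so the check applies the SAP's own rules to records.

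**Inputs**
- Ongoing status: D07 at least Grade 1 and post-D07 maximum at least Grade 1 (SAP 4.4.2.1.7).
- In-period count: graded days in D0 to D07 (SAP 4.4.2.1.5).
- Overall days if ongoing: (stop day − vaccination day) + in-period count − length of solicited period + 1 (SAP 4.4.2.1.6).
- Length of solicited period: 8, counting D0 to D07 inclusive.

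**Does the formula work on complete data?**
- Present from D0, stop D20: 20 + 8 − 8 + 1 = 21, correct.
- Onset D05, stop D14: 14 + 3 − 8 + 1 = 10, correct.
- A length of 7 would give 20 + 8 − 7 + 1 = 22 for the first record, so 8 is the consistent reading.

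**D07 blank.** Grade 2 on D0 to D06, D07 blank, post-D07 maximum Grade 2, stop D12.
- Current rule: not ongoing, stop date unused, 7 in-period days remain.
- Formula, if ongoing: 12 + 7 − 8 + 1 = 12. With D07 counted: 12 + 8 − 8 + 1 = 13.
- Even without the stop date, a graded post-D07 maximum means at least one further day, so at least 7 + 1 = 8. The 7 contradicts the subject's own record.

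**Post-D07 maximum blank.** Grade 1 on D0 to D07, post-D07 maximum blank, stop D12.
- Current rule: not ongoing, 8 in-period days remain.
- Formula, if every later day was graded: 12 + 8 − 8 + 1 = 13. The grade after D07 is unknown, so the record supports only a range of 8 to 13.

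**How the gap grows.** Reaction present every day from D0 until its stop date:

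| Stop day | Complete record | Current rule, D07 blank | Current rule, post-D07 maximum blank | Formula applied with D07 blank |
|---|---|---|---|---|
| D10 | 11 | 7 | 8 | 10 |
| D14 | 15 | 7 | 8 | 14 |
| D20 | 21 | 7 | 8 | 20 |
| D30 | 31 | 7 | 8 | 30 |

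A late onset can lose more in relative terms: onset D05, stop D14 and D07 blank leaves 2 days, against 10 with a complete record.

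**Which blanks matter.** Only the two key entries. With D03 blank and stop D20, the reaction is still ongoing and the result is 20 + 7 − 8 + 1 = 20, a loss of one day.

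**The case against.** Several objections have force.

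- **The 7 or 8 days is inferred.** SAP 4.4.2.1.6 gives no overall value for a non-ongoing reaction. This stands as a qualification: the figure follows from reading 4.4.2.1.5 and 4.4.2.1.6 together. No other value is offered, and the stop date is not used on any reading.
- **A stop date is not proof of a graded reaction.** Grade 1 redness or swelling starts at 25 mm (SAP Table 4.1), so a stop date may mark the end of a smaller reaction that the rule means to exclude. This stands for a blank post-D07 maximum and rules out simply trusting the stop date there. It does not answer the D07 case, where the post-D07 maximum is itself graded.
- **Missing entries are chased.** Diary pages are reviewed at the D30 visit (Protocol 5.1.4), incomplete entries are clarified with the subject (Protocol 11.1 and 13.2), and consistency checks are run (Protocol 11.2). This reduces the frequency but does not remove the gap.

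A reader might also infer more than the documents support:

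- **That a long-duration category is understated.** Neither document defines duration categories for solicited reactions. The listed endpoint is days of occurrence up to D07 (SAP 4.3.2.2), which comes from 4.4.2.1.5 and is not affected.
- **That giving Missing for an absent stop date is a second error.** It is a declared convention (SAP 4.4.2.1.6 and 5.3.1.5), and it is visible in the output.
- **That SAP 4.3.2.3.3 contradicts it,** because events without a stop date "will be considered as ongoing at the end of the study". That footnote concerns unsolicited events and does not govern solicited reactions.

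**Conclusion.** The concern holds in a narrow form. When the D07 grade or the post-D07 maximum is blank, the SAP reaches the same result as if it were None, and a known stop date after D07 goes unused. What remains is at most 7 days (D07 blank) or 8 days (post-D07 maximum blank), however late the stop date. The result is never too long, so the bias has one direction, and nothing in the output reveals it.

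The size in a single record can be large: 7 against 12 or 13 in the worked example, 7 against 31 for a reaction running to D30. These figures rest on a solicited period of 8 days, on the in-period count standing in for the overall count, and on the reaction lasting continuously to its stop date. For a blank post-D07 maximum the true value is only bracketed.

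The size for the trial cannot be estimated, because the documents give neither diary completeness nor the share of reactions passing D07; after diary queries it is probably low. Occurrence, maximum intensity over D0 to D07, time of onset and all immunogenicity results are unaffected. This is a minor correction to a descriptive derivation, worth making because it is cheap.

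**What to change.** Add two clauses to SAP 4.4.2.1.7:

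1. If the D07 intensity is Missing, but the last recorded intensity before it and the post-D07 maximum are both at least Grade 1, and a complete stop date after D07 exists, derive the reaction as ongoing and apply the 4.4.2.1.6 formula.
2. If the post-D07 maximum is Missing, D07 is at least Grade 1 and the stop date is after D07, set the overall number of days to Missing. Do not report the in-period count as the overall duration.

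Requiring a graded last entry in clause 1 keeps out a reaction that had already stopped. For example, Grade 1 on D0 to D02, None on D03 to D06, D07 blank and stop D12 stays not ongoing. Clause 2 avoids counting redness or swelling below 25 mm. A recorded None still ends the reaction, and the convention that a missing stop date gives Missing stays as it is.

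The cost is two SAP clauses, a small program change and a few more Missing overall durations.

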4.4.2.2 Unsolicited Non-serious Adverse Events

4.4.2.2.1 Presence

An observation will be considered an event if it has at least a verbatim term and is not Grade 0 (None) intensity event.

Grade 0 events will not be included in the analysis of the endpoint and should be included in the listing “Unsolicited non-serious adverse events not included in the safety analysis.”

4.4.2.2.2 Intensity

Intensity for unsolicited non-serious AE will be derived according to the following classification:

Grade 0 (None), Grade 1, Grade 2, Grade 3, or Missing (Unknown).

If the unsolicited non-serious AE is measurable and its preferred term is part of the list of solicited reactions, then the measurement is derived based upon and following the same rule as the intensity scales defined in the Section [4.4.2.1.1](#) for that measurable injection site or systemic reaction.

Intensity for the other unsolicited non-serious AEs will correspond to the value reported in the CRF.

The maximum intensity corresponds to the highest intensity for a unique term.

4.4.2.2.3 Last Vaccination

Last vaccination before any unsolicited non-serious AE is the study vaccination at Visit 1 (D0).

4.4.2.2.4 Time of Onset

Time of onset is derived from the start date of the unsolicited non-serious AE provided in the clinical database and the date of last vaccination:

Start date of the unsolicited non-serious AEs – date of last vaccination

The time of onset should be considered as missing only if one or both of the dates are missing or partially missing.

The unsolicited non-serious AEs will be analyzed “Within 30 days”, which corresponds to AEs with a time of onset between D0 and D30 after vaccination(s) or missing. An AE with missing time of onset will be considered to have occurred just within 30 days after the vaccination indicated by the visit number, so will be included in the safety analysis.

Note: Unsolicited non-serious AEs that occurred before vaccination (negative time of onset) or with onset higher than defined above (eg, > 30 days after vaccination[s]) will not be included in the safety analysis, but will be listed separately.

4.4.2.2.5 Duration

Duration is derived from the start and stop dates of the unsolicited non-serious AE provided in the clinical database:

Stop date of unsolicited non-serious AE - start date of unsolicited non-serious AE + 1.

The duration should be considered as missing only if 1 or both of the start and stop dates of the unsolicited non-serious AE is missing or partially missing.

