4.4.2.3.3 Duration

Duration will be computed using the same methodology as for unsolicited non-serious AEs described in Section 4.4.2.2.5.

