- 4) Percentage of subjects with titer ≥ 4 -fold rise from pre-vaccination to post-vaccination, and 95% CI
- 5) Percentage of subjects with rSBA vaccine seroresponse*

*rSBA vaccine seroresponse is defined as a post-vaccination titer $\geq 1:32$ for subjects with pre-vaccination rSBA titer $< 1:8$, or a post-vaccination titer ≥ 4 times the pre-vaccination titer for subjects with pre-vaccination rSBA titer $\geq 1:8$.

Data of subjects from MET50 (or MET43, if applicable) and MET59 will be combined and paired to evaluate antibody persistence and overall trends over 3-6 years post-priming with an MCV4 (ie, MenACYW conjugate vaccine-primed subjects or Menveo vaccine-primed subjects). If Menveo vaccine-primed subjects that were not part of MET50 are recruited, those will not contribute to the assessment of antibody persistence.

Safety

Safety results in Section 4.3.2.2 will be described for subjects in all study groups. The main parameters for the safety endpoints will be described by 95% CIs (Clopper-Pearson method) (14). Analyses will contain at least the descriptions listed in Table 5.2:

Table 5.2: Statistical analyses for safety observational objective

Safety Events	Time and Group	Description
Immediate unsolicited non-serious systemic AE	Within 30 minutes after vaccination(s) for all subjects in Groups 1 – 4	Percentage of subjects that have the event, MedDRA terms, intensity, relationship to vaccine, study discontinuation
Solicited injection site reactions	Within 7 days after vaccination(s) for all subjects in Groups 1 – 4	Percentage of subjects that have the event, onset, duration, intensity, action taken, study discontinuation, temperature collection routes
Solicited systemic reactions	Within 7 days after vaccination(s) for all subjects in Groups 1 – 4	Percentage of subjects that have the event, onset, duration, intensity, action taken, study discontinuation, temperature collection routes
Unsolicited non-serious AE/AR	Within 30 days after vaccination(s) for all subjects in Groups 1 – 4	Percentage of subjects that have the event, MedDRA terms, onset, duration, intensity, relationship, action taken, study discontinuation

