5.3.1.5 Start Date and Stop Date

Missing or partially missing start dates for unsolicited AEs will remain missing and not be imputed. If the start date is missing or partially missing, the time of onset will be considered to be missing. Nevertheless, unsolicited AEs with missing time of onset will be included in analyses according to the visit collected.

Missing or partially missing stop dates for AEs (solicited reactions and unsolicited AEs) will remain missing and not be imputed.

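### Events with no stop date get a missing duration in the SAP, so unresolved AEs leave the numeric duration summaries and cannot be told apart from data gaps

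*SAP*

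**What the plan says.** SAP 4.4.2.2.5 computes the duration of an unsolicited non-serious AE as stop date minus start date plus 1. It adds: "The duration should be considered as missing only if 1 or both of the start and stop dates" are missing or partial. For SAEs/AESIs, SAP 4.4.2.3.3 says "Duration will be computed using the same methodology as for unsolicited non-serious AEs", and SAP 4.4.2.4.3 says the same for MAAEs.

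For a solicited reaction still present when the solicited period ends, SAP 4.4.2.1.6 says: "If stop date of the solicited reaction is missing or incomplete (contains MD), the overall number of days of occurrence will be considered as Missing". SAP 5.3.1.5 sets the general rule: "Missing or partially missing stop dates for AEs (solicited reactions and unsolicited AEs) will remain missing and not be imputed".

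The footnote on stop dates in SAP 4.3.2.3.3, repeated in Protocol 9.3.2.3.3, says: "AEs for which no stop date was obtained during the course of the study will be considered as ongoing at the end of the study".

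Duration is a planned output. It is named in safety endpoints 1, 4, 5 and 6 (SAP 4.3.2.2). The row of SAP Table 5.2 for unsolicited non-serious AEs reads: "Percentage of subjects that have the event, MedDRA terms, onset, duration, intensity, relationship, action taken, study discontinuation".

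**The concern.** Whether a duration is missing here depends on the duration itself. An event that never resolves has no stop date and so gets no number, while an event that resolves quickly normally gets one. A summary of known durations is therefore a summary of resolved events, and it will tend to look shorter than the full set.

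The status the SAP has already assigned (ongoing) is also not carried into the duration tables. An AE that was still present and an AE whose stop date was simply not reported end up in the same state. For unsolicited non-serious AEs no other planned summary separates them. What is at stake is the description of how long adverse events last after the booster; no hypothesis test is involved.

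**Working it through.** The plan states no figure on this point, so there is nothing to reproduce. The check is to follow the derivation rules for each event type and see what survives when no stop date exists.

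**What is lost and what remains**

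- *Unsolicited non-serious AEs.* Duration is missing (SAP 4.4.2.2.5). The Table 5.2 row lists no outcome, and the SAP derives no ongoing variable for these events. Occurrence counts remain.
- *SAEs/AESIs and MAAEs.* Duration is missing (4.4.2.3.3, 4.4.2.4.3). Outcome is summarised for both in Table 5.2, so non-resolution can still be seen there.
- *Solicited reactions.* The overall number of days is missing (4.4.2.1.6). The day count within D0 to D07 needs no stop date: "It corresponds to the number of days with 1 of daily intensities of Grade 1, Grade 2, or Grade 3" (4.4.2.1.5). An ongoing flag is derived in 4.4.2.1.7.
- *Immediate AEs.* Endpoint 1 names duration, but the matching row of Table 5.2 does not list it.

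The SAP defines no duration categories for unsolicited AEs and does not say whether the tables will carry a row for missing durations. For action taken, 4.4.2.5.2 says that missing observations are included in the summary; the duration sections say nothing similar.

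**What is known about an AE with no stop date**

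Apply the SAP formula with the last recorded status in place of the stop date: minimum duration = last day with status recorded − onset day + 1. Onset lies between D0 and D30 (SAP 4.4.2.2.4). The D30 visit falls between D30 and D44, and the last call between D180 and D194.

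- Status last recorded at the D30 visit: from 30 − 30 + 1 = 1 day (onset D30, visit D30) to 44 − 0 + 1 = 45 days (onset D0, visit D44).
- Status recorded at the last call: from 180 − 30 + 1 = 151 days to 194 − 0 + 1 = 195 days.

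Which range applies depends on what was asked. Protocol 5.1.4 has the last call ask about SAEs since vaccination and MAAEs since the D30 visit. It does not ask whether a non-serious AE without medical attendance is still present. For those events the first range may be all that the data support.

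**Solicited reactions**

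The formula in 4.4.2.1.6 is (stop day − vaccination day) + days of occurrence within the solicited period − length of the period + 1, with a length of 8 days (D0 to D07).

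- Present on all 8 days, stop on D10: 10 + 8 − 8 + 1 = 11 days.
- Present on D0, absent D1 to D6, present again on D07, stop on D10: 10 + 2 − 8 + 1 = 5 days. An elapsed interval would give 10 − 0 + 1 = 11.

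So the formula works when a stop date exists. The variable counts days with the reaction, and an elapsed time from start to last contact is not a valid substitute for it.

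**Size**

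The shift in any duration summary depends on the share of events with no stop date and on the durations of the resolved events. Neither is in the documents.

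**The case against.** The strongest reply is that the footnote and the duration rule do not conflict. One gives a status and the other says the number of days is unknown, and both can be true. Declining to impute is a pre-specified and consistent choice for descriptive tables. This stands: the defect is that the status is not carried into the duration summary, and reporting it there imputes no stop date.

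A second reply is that a missing stop date is not proof of persistence. Stop dates are actively sought only for related AEs (SAP 4.3.2.3.3); for others the investigator supplies one when it becomes available. This also stands. A reader might infer that every such AE is known to have lasted until the D180 call. The documents do not support that, because the call does not ask about non-serious AEs without medical attendance.

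A third reply is that related AEs, and AEs that led to discontinuation, are followed until resolution, stability or chronicity (Protocol 5.1.4). This helps only in part, since a related AE that becomes chronic still has no stop date.

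A fourth reply is that solicited reactions are largely protected. That is right. A reader might infer that the longest-lasting reactions disappear from the solicited-reaction tables, but the D0 to D07 day count and the ongoing flag both survive.

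**Conclusion.** The point holds as a limited one about descriptive safety summaries. As written, unresolved unsolicited AEs, SAEs/AESIs and MAAEs contribute no numeric duration and cannot be separated from data gaps in the duration output. The consequence is greatest for unsolicited non-serious AEs, where no outcome summary is planned.

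Occurrence counts, the SAE and MAAE outcome summaries and the primary immunogenicity analysis are untouched. For solicited reactions only the overall number of days is affected.

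The direction, towards shorter apparent durations, rests on the assumption that at least some events without a stop date are truly unresolved. The size cannot be derived. It may be tempting to quote a percentage shift in some longest-duration category, but the documents define no such category and supply no inputs for the calculation.

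**What to change.** In SAP 4.4.2.2.5, 4.4.2.3.3 and 4.4.2.4.3, report events with a known start and no stop date in their own category of the duration tables, labelled 'ongoing / no stop date obtained'. Keep 'missing' for an unknown start or partial dates. SAP 5.3.1.5 can stand, since no stop date is imputed.

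If a minimum duration is shown, count it only to the last contact at which the status of that event was recorded, and flag it as a minimum. For non-serious AEs without medical attendance this may be the D30 visit.

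In SAP 4.4.2.1.6, show a reaction that is flagged ongoing under 4.4.2.1.7 and has no stop date as 'ongoing', with its D0 to D07 day count as the lower bound. Do not use last contact minus start plus 1 for this variable.

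The cost is SAP wording and a small programming change on dates already held. The downside is that some resolved events whose stop date was never reported will sit in the ongoing category, so a table footnote should say so.
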